### Definition of terms

a **Cardiac ischaemic symptoms:** chest pain or discomfort or equivalent (eg, neck or jaw symptoms, dyspnoea believed to represent an angina pectoris equivalent) believed due to impaired coronary flow secondary to atherosclerotic disease.

b **At rest:** started with exercise or spontaneously and did not resolve with rest.

c **Development of pathological Q waves:** development of any new or presumed new Q waves that are  $\geq 0.03$  sec in width and  $\geq 1$  mm (0.1 mV) in depth in at least 2 contiguous leads.

d **Myocardial necrosis biomarker evidence of acute MI - any of the following:** maximal concentration of Troponin exceeding the 99th percentile of the values for a reference control group. Elevations should be seen on at least one occasion but preferably with a rising or falling pattern during the first 24 hours following the index clinical event. The coefficient of variation (CV; imprecision) at the 99th percentile should be lower or equal to 10%. Otherwise, the concentration at the 10% CV should be regarded as the diagnostic cut-off. For cardiac troponin T the diagnostic cut-off is equal to or greater than 0.03  $\mu\text{g/L}$ . Cut-offs for cardiac Troponin I assays vary among different manufacturers and should be read-off from approved tabulations.

e **ECG changes indicative of ischaemia - any of the following:** ST-segment elevation: new or presumed new ST-segment elevation  $\geq 1.0$  mm (0.1 mV) in 2 or more contiguous leads.

New or presumed new ST-segment depression of  $\geq 0.5$  mm ( $\geq 0.05$  mV) in 2 or more contiguous leads.

New or presumed new T-wave abnormalities - inversion of  $\geq 1$  mm (0.1 mV) in 2 or more contiguous leads.

f **Laboratory upper normal limit:** This is the value that is considered abnormal. For institutions that report an intermediate or indeterminate range for Troponin I or T, these values are considered abnormal for this study.

**Procedure in case of recurrent cardiac ischemic symptoms:** If the patient experiences cardiac ischemic symptoms  $\geq 20$  minutes at rest, he/she will be treated in accordance with local practice and the following procedures will be performed:

- Cardiac biomarkers of necrosis (troponin) should be measured locally approximately every 8 hours for at least 24 hours
- A standard 12-lead electrocardiogram should be obtained during or as soon after the episode of ischemia as possible and 24 hours after resolution of symptoms.

### 6.3.2.2 Stroke/TIA

#### Definition:

A **stroke** is defined as a neurological deficit caused by an ischaemic or haemorrhagic central nervous system event with residual symptoms at least 24 hours after onset or leading to death, confirmed by imaging.

Stroke will be further sub-classified as:

- **Haemorrhagic:** a stroke with documentation of intracranial haemorrhage on imaging (eg, computed tomography (CT) scan or magnetic resonance imaging (MRI) scan) either in the cerebral parenchyma, or a subdural, epidural or subarachnoid haemorrhage. Evidence of haemorrhagic stroke obtained from lumbar puncture, neurosurgery, or autopsy can also confirm the diagnosis.
- **Ischaemic:** a stroke that results from a thrombus or embolus impairing central nervous system perfusion (and not due to haemorrhage). Haemorrhagic conversion of an ischaemic stroke that becomes symptomatic should be recorded as a new haemorrhagic stroke event.
- **Unknown/No imaging performed:** if the type of stroke could not be determined by imaging or other means (from lumbar puncture, neurosurgery, or autopsy).

A **TIA** is defined as a focal neurological deficit that resolves spontaneously without any evidence of residual deficit by 24 hours. For inclusion in the first secondary composite efficacy endpoint the TIA must either require hospitalisation if an outpatient or prolong hospitalisation if an inpatient or have objective confirmation of cerebrovascular disease.

**Procedures in case of focal neurological symptoms** (ie, potentially representing stroke or transient ischemic attack). If the patient experiences focal neurological symptoms, he/she will be treated in accordance with local practice and the following procedures will be performed:

- Complete neurologic exam
- Brain imaging [computed tomography (CT) or magnetic resonance imaging (MRI)]

### 6.3.2.3 Urgent Coronary Revascularization

#### Definition:

Urgent Coronary Revascularization is defined as repeated PCI or CABG within 24 hrs after a new ischemic event of the culprit vessel of the index event.

**Procedures in case of Coronary Revascularization** (ie, percutaneous coronary intervention or coronary-artery-bypass grafting): If the patient experiences urgent coronary revascularization, he/she will be treated in accordance with local practice and the following procedures will be performed:

- Cardiac biomarker of necrosis (Troponin) should be measured locally immediately before the procedure and approximately every 8 hours for at least 24 hours after the procedure
- A standard 12-lead electrocardiogram should be obtained before the procedure and in the morning following the procedure.
- For patients undergoing CABG, the number of packed red blood cell or whole blood transfusions and the chest tube output in the first 24 hours should be noted

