## 1.2 Research hypothesis

Results from PLATO study support ticagrelor as a new standard of care for the management of patients with STEMI intended for PCI. Treatment should be initiated with a single 180 mg loading dose (two tablets of 90 mg) and then continued at 90 mg twice daily. However, the optimal timing for the initiation of treatment with ticagrelor has not been determined as in PLATO patients were initiated on treatment if they presented within 24 hours of symptoms onset.

It is hypothesized that earlier (pre-hospital) initiation of ticagrelor could result in rapid restoring of coronary flow and myocardial reperfusion—as assessed by the co-primary endpoint of TIMI flow grade 3 of MI-related vessel at initial angiography or a  $\geq 70\%$  ST-segment resolution pre-PCI—, and thus may facilitate PCI procedure and hence improve clinical outcome

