## **2.2 Secondary objectives**

To compare the efficacy of pre-hospital vs. in-hospital initiation of ticagrelor therapy by assessing the following endpoints:

- Composite of death, MI, stroke, urgent revascularization and acute stent thrombosis during 30 days of study
- Composite of death, MI, urgent revascularization during 30 days of study
- Acute stent thrombosis during 30 days of study
- Thrombotic bail-out with GPIIb/IIIa inhibitors at initial PCI
- Complete ( $\geq 70\%$ ) ST-segment elevation resolution at 60 min post-PCI
- Corrected TIMI frame count (cTFC) at angiography, pre and post PCI.
- TIMI myocardial perfusion grade (TMPG) at angiography, pre and post PCI.
- Time–relationship (from symptom onset to 1st dose intake ) on each co-primary
- Time–relationship (from 1st dose intake to ECG/ angiography) on each co-primary
- TIMI flow grade 3 at end of procedure.

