#### **3.1 Overall study design and flow chart**

This is a 30 day, international, randomized, parallel-group, double-blind, placebo-controlled phase IV study to evaluate the efficacy and safety of pre-hospital vs. in-hospital initiation of ticagrelor therapy in STEMI patients planned for primary PCI ; this concerns as well patients (not pre-treated for their STEMI) in emergency rooms of non-PCI hospitals. The qualifying ECG and inclusion into the study are made solely by the ambulance personnel.

The 30 day active treatment period will be followed by a safety monitoring period of 7 days.

[figure not shown]
After validation of eligibility criteria, patients will be randomized to one of two groups:

- Pre-hospital ticagrelor arm: patients will receive a loading dose of 180 mg ticagrelor for pre-hospital administration followed by placebo in the hospital before angiography.
- In-hospital ticagrelor arm: patients will receive a placebo in the ambulance followed by loading dose of 180 mg ticagrelor in the hospital before angiography.

Approximately 12 hours after the second loading dose, the patient will continue on ticagrelor 90 mg BID as maintenance treatment and will be followed in study for 30 days post randomisation.

Please refer to the study flow chart (Figure 1)

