## **11. EVALUATION AND CALCULATION OF VARIABLES**

### **11.1 Calculation or derivation of efficacy variables**

ECG and angiographic assessments will be centrally measured.

The co-primary endpoint from ECG, complete ST –segment elevation resolution will evaluate the percentage of patients with an ST-segment elevation resolution  $\geq 70\%$  derived from percentage change in ST- segment elevation between ambulance assessment and in-hospital assessment pre-PCI.

The co-primary endpoint from angiography, TIMI flow grade 3 will evaluate the percentage of patients reaching TIMI flow grade 3 at initial angiography, issued from TIMI flow data, all grades.

Binary (yes/no) variables patients will be created and classified according to whether the specified event occurred.

Events related to secondary binary endpoints including complete ( $\geq 70\%$ ) ST-segment elevation resolution at 60 minutes post PCI, TIMI flow grade 3 at end of procedure, Thrombotic bail-out with GPIIb/IIIa inhibitors at initial PCI will be classified in the same way.

Length of time variables will be derived as the number of minutes from the onset to the end of the time interval considered. These intervals include time from symptom onset to first study medication administration and time from first study drug administration to time of ECG/angiography.

For the other endpoints, in each case patients will be classified (yes/no) according to whether one or more the events considered occurred during the 30 days of study. This includes the composite of death, MI, stroke, urgent revascularization, acute stent thrombosis and a similar composite including death, MI, and urgent revascularization.

Continuous variables measured by core lab include the correct TIMI frame count (cTFC) at angioplasty pre and post PCI and the ordinal TIMI myocardial perfusion grade (TMPG) at angioplasty pre and post PCI.

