### **12.1 Description of analysis sets**

#### **12.1.1 Efficacy analysis set**

The Modified Intent to Treat Population (mITT) will include all randomized patients who received a dose of study medication. Patients will be classified according to the treatment group they were randomized to. All efficacy endpoints will be analyzed using the mITT population.

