## **12.3 Determination of sample size**

Since, based on multiplicity procedure, the initial significance level is 2.5%, the sample size calculation will be based on a significance level of 2.5% and 80% power. Sample size calculations were derived using nQUERY7.

The sample size for the two co-primary endpoints is derived from the ST Resolution hypothesis. However, the study is enough powered for the 2 criteria when considering the table below.

The ST segment deviation was previously studied in On Time2 study (Van't Hof Aw et al 2008), where complete ST resolution occurred in 20.7% of patients in the pre-hospital GP I Ib/IIIa group versus 15.4% in the non GP I Ib/IIIa group, all patients receiving a clopidogrel loading dose. This last number, corresponding to an in-hospital group was confirmed in Assent 4 PCI study where electrocardiographic reperfusion was shown in 14.9% of patients.

Based on this data, it is hypothesized that 15% of patients in the in-hospital group will achieve complete ST elevation resolution versus 21% in the pre-hospital group (absolute difference of 6%). Taking into account a significance level of 2.5%, 779 evaluable patients are required in each treatment group to have 80% power using a two group chi squared test of equal proportions. Assuming a 12% dropout for invaluable or missing ECG criteria, a total of 1770 patients are required to be enrolled in the study to assess the ST segment elevation resolution difference.

To insure the sample size is adequate for the analysis of the co-primary endpoint TIMI Grade at initial angiography, values ranging from 15-27% were reported in various studies. Clinicians agreed that a 30 to 35% relative difference between the 2 groups is clinically relevant. In order to hypothesize on the various degree of angiographic reperfusion expected the following table was created to show a range of hypothesis and the related sample size. A statistical difference can be shown for the highlighted hypothesis (in bold) in the table. Dropout rate at initial angiography is assumed to be low, and less than 8%. These values indicate the sample size of 1770 patients is adequate for this endpoint.

	Assumptions with TIMI flow grade3 = 15% in in-hosp group		Assumptions with TIMI flow grade3 = 27% in in-hosp group	
Assumptions of relative difference (%) between the two groups	30	35	30	35
In-hosp group	15%	15%	27%	27%
Pre-hosp group	19.5%	20.3%	35.1%	36.5%
N per group with alpha=0.05	1106	826	512	376

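### Urgent revascularization requires a repeated PCI, so an urgent first PCI in a patient who had no index PCI does not count for that component

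*Protocol*

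**What the plan says.** Section 6.3.2.3 of the protocol holds its only definition of urgent coronary revascularization, which "is defined as repeated PCI or CABG within 24 hrs after a new ischemic event of the culprit vessel of the index event". Nothing there or elsewhere says how to classify a patient who had no PCI at the initial angiography.

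The component feeds two secondary endpoints. Section 2.2 lists the shorter one as "Composite of death, MI, urgent revascularization during 30 days of study". Section 11.1 derives both yes/no per patient: "This includes the composite of death, MI, stroke, urgent revascularization, acute stent thrombosis and a similar composite including death, MI, and urgent revascularization".

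Section 3.1 describes the comparison as "pre-hospital vs. in-hospital initiation of ticagrelor therapy in STEMI patients planned for primary PCI". Randomisation takes place before hospital arrival (5.2.1), and no entry criterion requires that PCI is actually done. The mITT set in 12.1.1 "will include all randomized patients who received a dose of study medication".

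Section 6.3.2 tells investigators to apply these definitions when they assess possible endpoints. Section 6.4.5, as revised by Administrative Change 4, sends suspected cardiac ischaemic events that do not meet an endpoint definition to AE/SAE reporting instead of central adjudication.

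**The concern.** A first PCI is not a repeated one. Take two dosed patients who each have a new ischaemic event of the index culprit vessel, treated by PCI within 24 hours. If the first had an index PCI, the event counts as urgent revascularization. If the second had angiography only, it does not. The outcome definition therefore depends on a procedure that follows randomisation.

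The word is also ambiguous for CABG. If it applies to CABG, a first urgent CABG may fail the definition. If it does not, a first urgent CABG counts where a first urgent PCI does not. The same section asks for transfusion and chest-tube data after CABG, so CABG was evidently expected to occur, but the sentence does not settle the question.

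At stake are completeness and uniform classification of one component of two secondary composites. Because investigators screen against this wording, a literal reader could keep such an event out of the endpoint package altogether.

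**Working it through.** **1. Can the episode count some other way?** Comparing the definitions for a patient without index PCI:

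- MI (6.3.2.1) needs no earlier PCI. Within 18 hours of index onset, new ST elevation plus at least 20 minutes of symptoms at rest is enough. After that, until biomarkers normalise, it takes a troponin rise of at least 50% over a falling value, plus symptoms or an ECG change. Once they have normalised, a new biomarker elevation with symptoms, ECG change or pathology qualifies. The limb for MI within 24 hours after PCI can also apply to the urgent PCI itself.
- Stent thrombosis (6.3.2.4) cannot describe the triggering event if no stent had been placed.
- Death counts in its own right.

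What is lost from the composites is therefore an urgent first PCI that misses every MI limb, in a patient with no other component event. An example is ischaemia with ST depression only, treated promptly, without the required troponin pattern.

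**2. Patients per arm.** The protocol gives no figure for this component, so the only stated figure to reproduce is the sample size (12.3). It assumes that "15% of patients in the in-hospital group will achieve complete ST elevation resolution versus 21% in the pre-hospital group", with two-sided alpha 0.025 and 80% power:

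n = [2.2414 × √(2 × 0.18 × 0.82) + 0.8416 × √(0.15 × 0.85 + 0.21 × 0.79)]² / 0.06² = 778.1, so 779 per arm, as stated. With 12% dropout, 2 × 779 / 0.88 = 1770.5, against the stated 1770. Per arm: 1770 / 2 = 885.

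**3. Uncounted events per arm, before MI overlap.** Let q be the share without index PCI and r the share of those with an urgent first PCI by day 30. Neither is in the protocol; the values are assumptions.

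- q = 5%, r = 3%: 885 × 0.05 × 0.03 = 1.3
- q = 10%, r = 5%: 885 × 0.10 × 0.05 = 4.4
- q = 15%, r = 8%: 885 × 0.15 × 0.08 = 10.6

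The net loss is each figure × (1 − m), where m is the share that also meets the MI definition or has another component event. The protocol does not allow m to be estimated.

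**4. Could the arms differ?** This needs a further assumption: that a share f of patients reperfused before PCI then have no index PCI. Uncounted events per arm are 885 × (reperfused share) × f × r. The reperfused shares are the planning rates in 12.3; f and r are assumed.

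| Planning rates, in- vs pre-hospital | f = 5%, r = 2% | f = 20%, r = 5% | f = 50%, r = 10% |
|---|---|---|---|
| ST resolution 15% vs 21% | 0.13 vs 0.19 | 1.33 vs 1.86 | 6.64 vs 9.29 |
| TIMI 3, 15% vs 19.5% | 0.13 vs 0.17 | 1.33 vs 1.73 | 6.64 vs 8.63 |
| TIMI 3, 27% vs 36.5% | 0.24 vs 0.32 | 2.39 vs 3.23 | 11.95 vs 16.15 |

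The differences run from 0.04 to 4.2 patients, and from 0.4 to 0.8 in the middle column (0.05 to 0.10 percentage points of 885). Taking instead an assumed 12% vs 10% without index PCI and r = 5%, the difference is 885 × 0.02 × 0.05 = 0.9 patients, or 0.1 points.

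For scale, at an assumed composite rate of 4% the standard error of the arm difference is √(2 × 0.04 × 0.96 / 885) = 0.0093. That is 0.93 points, or about 8 patients.

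**The case against.** The best defence is that little is lost. Re-occlusion of the culprit vessel is largely what the MI definition describes, and MI is in both composites. The composites are secondary: the Holm procedure in 12.2.1 covers only the co-primaries. Events that miss the definition are still recorded as AEs/SAEs, so a sensitivity analysis is possible. The endpoint manual and the adjudication charter, neither of which is shown, may read the word loosely as any subsequent procedure.

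Most of this stands, and it sets the size of the point. It does not close the gap. The protocol text is what investigators are told to apply, and Administrative Change 4 sends what does not fit it away from adjudication. If the manual or charter reads it differently, the protocol should say the same.

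A reader might go further and infer bias towards the pre-hospital arm. Section 1.2 hypothesises that "earlier (pre-hospital) initiation of ticagrelor could result in rapid restoring of coronary flow and myocardial reperfusion", so more patients there might have an open vessel and no index PCI. The documents do not support that step. Nowhere do they say that early flow leads to PCI being omitted. Sections 1.2, 1.3 and 3.2 say that it may facilitate PCI, and the rationale concerns patients who undergo PCI with the vessel already open. The planning rates are reperfusion rates, not rates of omitted PCI.

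A reader might also express the uncounted events as a fraction of the composite. That would mislead: the counts are before MI overlap, and the composite rate is itself an assumption.

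**Conclusion.** The wording gap is real and minor. Read literally, the definition does not count an urgent first culprit-vessel PCI in a dosed patient without index PCI, counts the same event after index PCI, and leaves CABG unclear. The claim holds for this component only; in the composites the loss is limited to episodes that miss every MI criterion.

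The number is probably a few per arm at most. It cannot be derived from the protocol: the central assumed values give about 1 to 4 per arm of 885 before MI overlap. The larger results, 10.6 and 16.15, need the highest assumed values together and no overlap. A difference between arms is possible in principle, but it rests on assumptions alone, and its central size of under one patient is small against a standard error of about 8. The co-primary endpoints, their testing and the sample size are not affected.

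**What to change.** In section 6.3.2.3, replace the words from *repeated* to *CABG* with: *any PCI or CABG performed after the end of the initial angiography/PCI procedure, whether or not PCI was done at that procedure*. Leave the rest of the sentence as it is. The existing requirement of a new ischaemic event of the index culprit vessel within the preceding 24 hours already keeps planned deferred PCI out, so a further qualifier such as *unplanned* is not needed. The new phrase also settles the CABG question.

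Align the endpoint manual for investigators and the adjudication charter with the same wording. The cost is one phrase in the protocol and matching text in those two documents, with no added visits, patients or data collection and no change to patient management.

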#### **6.3.2.4 Stent Thrombosis**

##### **Definition according to Academic Research Consortium - Mauri et al 2007**

- Definite stent thrombosis required the presence of an acute coronary syndrome with angiographic or autopsy evidence of thrombus or occlusion.
- Probable stent thrombosis included unexplained deaths within 30 days after the procedure or acute myocardial infarction involving the target-vessel territory without angiographic confirmation.
- Possible stent thrombosis included all unexplained deaths occurring at least 30 days after the procedure.

#### **6.3.2.5 Bail-out use of GPIIb/IIIa receptor antagonists**

##### **Definition**

Bail-out treatment is to provide GPIIb/IIIa inhibition with IIB/IIIa inhibitors urgently during the course of an interventional procedure in the event of abrupt closure, no reflow, side branch closure, or other bail-out situations.

#### **6.3.2.6 Death**

##### **Definition**

All cause deaths reported until 30 days post-randomisation will be recorded as clinical endpoints. They will not be adjudicated. The cause of death will be reported in the SAE form or in bleeding/stroke or cardiac-ischemic event form of the eCRF, according to the definition of Adverse Event (see section 6.4.1).

In the eCRF, death will be further sub-classified by vascular or non-vascular primary cause. Death from vascular causes includes cardiovascular deaths, cerebrovascular deaths, deaths from any other vascular abnormality or deaths for which there was no clearly documented nonvascular cause. Some specific examples are given below:

Vascular death: sudden death, MI, other CAD, stroke, arterial embolism, pulmonary embolism, ruptured aortic aneurysm, aortic dissection, heart failure, cardiac arrhythmia or death from bleeding (not related to trauma).

Non-vascular death: cause of death was respiratory failure, pneumonia, cancer, trauma, suicide, sepsis, multi-organ failure or any other clearly defined cause (eg, liver failure or renal failure).

For Drug Safety reporting purposes any death with unknown/uncertain cause should be reported as death, if the cause of death becomes known, then the cause is reported as the SAE.

